2.3.1. Risk Assessment

Potential Risk of Clinical Significance	Summary of Data/Rationale for Risk	Mitigation Strategy
	Investigational Product (IP) [GSK2982772]	
Central Nervous System (CNS) effects	Non-clinical data: In initial 4-week nonclinical toxicology studies, neurological-related events (uncoordinated movement, irregular gait, trembling, hunched appearance and decreased activity) were observed in some rats and monkeys. In 13-week nonclinical toxicology studies, no neurological-related events were observed in rats or monkeys. In the 39-week good laboratory practice (GLP) toxicology study, there were no CNS findings observed in monkeys administered 6, 20 or 60 mg/kg/day. Clinical data: No drug-associated CNS adverse events reported in clinical studies.	 Participant Selection: Participants with known history of significant neurologic disorders including but not limited to progressive multiple sclerosis (MS), Amyotrophic lateral sclerosis (ALS), Alzheimer's and dementia will be excluded. Individuals with potentially increased susceptibility for neurologic effects will be excluded based on medical history at Screening. Participant Monitoring: Participants will be monitored for standard CNS-related AEs.
CNS suicidality	GSK2982772 is considered to be a CNS-active drug based on pre-clinical studies. Clinical data:	Participant selection: • Participants with a current history of Suicidal Ideation Behaviour (SIB) as measured using the Columbia Suicide Severity Rating Scale (C-SSRS) or a

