2.3.3. Overall Benefit: Risk Conclusion

Taking into account the measures taken to minimize risk to participants participating in this study, the potential risks identified in association with GSK2982772 are justified by the anticipated benefits that may be afforded to participants with psoriasis by contributing to the understanding of the disease and the development of new therapies for patients with these conditions in the future.

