5. STUDY POPULATION

Prospective approval of protocol deviations to recruitment and enrollment criteria, also known as protocol waivers or exemptions, is not permitted.

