 - Please note: In cases where the QuantiFERON-TB Gold Plus test is indeterminate, the participant may have the test repeated once, but they will not be eligible for the study unless the second test is negative, or they have a negative tuberculin skin test (defined as skin induration <5 mm at 49 to 72 hours, regardless of Bacillus Calmette-Guerin or other vaccination history). There must be no other clinical evidence of TB on physical examination of the participant at Screening.
- 6. Current or history of liver disease, known hepatic or biliary abnormalities (with the exception of Gilbert's syndrome or asymptomatic gallstones).
- 7. Current or history of renal disease.

- 8. Significant unstable or uncontrolled cardiovascular disease including uncontrolled hypertension.
- 9. Hereditary or acquired immunodeficiency disorder, including immunoglobulin deficiency.
- 10. History of major organ transplant (e.g., heart, lung, kidney, liver) or hematopoietic stem cell/marrow transplant.
- 11. Planned surgical procedure that makes the participant unsuitable for the study, in the opinion of the Investigator.
- 12. History of malignant neoplasm within the last 5 years, except for adequately treated cancers of the skin (basal or squamous cell carcinoma) or carcinoma in situ of the uterine cervix that has been fully treated and shows no evidence of recurrence after at least 12 months following treatment.
- 13. History of significant progressive neurologic disorders including, but not limited to, progressive MS, ALS, Alzheimer's and dementia.
- 14. History of a medical condition other than plaque psoriasis, or other considerations, which may confound interpretation of efficacy or safety study data, or put the participant at unacceptable risk, in the opinion of the Investigator.

Prior/Concomitant Therapy

- 15. History of lack of primary response to anti-TNF biologic therapies (either approved or experimental) at approved doses (or at the doses received if experimental therapies) after at least 3 months of therapy.
- 16. Participant has previous exposure to 3 or more biologic therapies of any mechanism of action.
- 17. Treatment with the prohibited therapies listed in Section 6.4.1, or changes to those treatments, within the specified timeframe. If in doubt, or the therapy is not listed please consult with the medical monitor.

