9.2. Sample Size Determination

Approximately 32 participants will be screened to achieve 21 randomly enrolled to either GSK2982772 or placebo in a 2:1 allocation ratio. Replacement participants may be randomised (up to approximately 6) into the study at the discretion of the Sponsor, to ensure that approximately 21 have completed the Week 4 visit.

The primary efficacy endpoint is PASI75 response (achieving ≥75% improvement from Baseline in PASI score)at Week 12. The sample size is based on the difference in PASI75 response rates between GSK2982772 960 mg and placebo.

At Week 12, the expected PASI75 response rate on placebo is approximately 7%. This value represents typical responses seen in this indication [Papp, 2018; Checchio, 2017].

The study will leverage historical placebo data to reduce the uncertainty in the placebo response rate and thus improve operating characteristics of the trial. The historical placebo data will be combined with the trial data via a Bayesian analysis.

With a sample size of 21 participants there is approximately 99% probability of achieving a >97.5% posterior probability that the true treatment difference over placebo >0%, based on an assumed placebo response of 7% and an assumed true treatment difference of 55% and incorporating informative historical placebo data into the analysis. For the placebo arm an informative Beta (3.5, 46.5) distribution with an effective sample size of 50 participants was used. For the active arm a vague Beta (1/3, 1/3) prior is used.

An equivalent power calculation, assuming placebo response of 7% and using a two-sided significance level of 0.05, the proposed sample size of 21 participants gives >90% power to detect a 55% difference in PASI75 response rates between GSK2982772 960 mg versus placebo at Week 12 using a Newcombe score test [Newcombe, 1998] (assuming no historical data is borrowed).

No sample size re-estimation is planned for this study.

Note: "Enrolled" means a participant's, or their legally acceptable representative's, agreement to participate in a clinical study following completion of the informed consent process. Potential participants who are screened for the purpose of determining eligibility for the study, but do not participate in the study, are not considered enrolled, unless otherwise specified by the protocol.

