10.2. Appendix 2: Clinical Laboratory Tests

- The tests detailed in Table 3 will be performed by the central laboratory.
- Local laboratory results are only required in the event that the central laboratory results are not available in time for either study intervention administration and/or response evaluation. If a local sample is required, it is important that the sample for central analysis is obtained at the same time.
- Protocol-specific requirements for inclusion or exclusion of participants are detailed in Section 5 of the protocol.
- Additional tests may be performed at any time during the study as determined necessary by the Investigator or required by local regulations.
- Pregnancy Testing
 - Refer to Section 5.1 Inclusion Criteria for Screening pregnancy criteria.
 - Pregnancy testing will be conducted as appropriate per Section 1.3 Schedule of Activities.
 - Additional serum or urine pregnancy tests may be performed, as determined necessary by the Investigator or required by local regulation, to establish the absence of pregnancy at any time during the participant's participation in the study.

 Table 3
 Protocol-Required Safety Laboratory Assessments

Laboratory Assessments	Parameters						
Hematology	Platelet Count RBC Count Hemoglobin Hematocrit	Red blood ce Indices: Mean corpus volume (MCV Mean corpus hemoglobin (I		uscular CV) uscular	Oiffer Neutr Lymp Mono	e blood cell C) count with rential: rophils phocytes poytes pophils phils	
Clinical Chemistry ¹	Blood urea nitrogen (BUN)	nitrogen (BUN)		Aspartate Aminotransferase (AST)/ Serum Glutamic- Oxaloacetic Transaminase (SGOT)		Total and direct bilirubin	
	Creatinine			Alanine Aminotransferase (ALT)/ Serum Glutamic-Pyruvic		Total Protein	

Laboratory Assessments	Parameters				
			Transaminase (SGPT)		
	Glucose ²	Calcium	Alkaline phosphatase	Albumin	
	Triglycerides ²	Total cholesterol ²	High Density Lipoproteins (HDL) cholesterol ²	Low Density Lipoproteins (LDL) cholesterol ²	
	Glycated haemoglobin (HbA1c)	Insulin ²			
Routine Urinalysis	 Specific gravity pH, glucose, protein, blood, ketones by dipstick Microscopic examination (if blood or protein is abnormal) 				

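### Section 2.3.1 promises to exclude significant neurologic disorders, but exclusion criterion 13 covers only the progressive ones

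*Protocol*

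**What the plan says.** The CNS effects row of the risk table (Protocol 2.3.1) records that in the initial 4-week toxicology studies "neurological-related events (uncoordinated movement, irregular gait, trembling, hunched appearance and decreased activity) were observed in some rats and monkeys". Under participant selection, the row says that a defined group will be excluded: "Participants with known history of significant neurologic disorders including but not limited to progressive multiple sclerosis (MS"), ALS, Alzheimer's and dementia. A second sentence adds that people who may be more susceptible to neurologic effects will be excluded on the basis of their medical history at Screening.

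Criterion 13 in Protocol 5.2 reads: "History of significant progressive neurologic disorders including, but not limited to, progressive MS, ALS, Alzheimer's and dementia".

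Criterion 14 follows it and is general. It covers "History of a medical condition other than plaque psoriasis, or other considerations, which may confound interpretation of efficacy or safety study data", or which may put the participant at unacceptable risk, and it is left to the Investigator's opinion. Section 5 rules out waivers: "Prospective approval of protocol deviations to recruitment and enrollment criteria, also known as protocol waivers or exemptions, is not permitted". The benefit-risk conclusion in 2.3.3 is introduced with the words "Taking into account the measures taken to minimize risk to participants participating in this study".

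**The concern.** The protocol describes the same safety measure twice, with different scope. The risk table states an unconditional exclusion of a broad class. The criterion that sites check against states an exclusion of a subset of that class. A person whom the risk table says will be kept out can pass criterion 13.

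At stake is whether the measure behind the benefit-risk conclusion is the one actually applied. The sponsor regards the compound as CNS-active (2.3.1 and 8.2.5). The animal signs in the CNS row, such as poor coordination and trembling, are not peculiar to progressive disease, and nothing in the row explains why only progressive disorders should matter. In a multicentre trial, sites could also reach different decisions about the same kind of patient.

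**Working it through.** No figure in the plan is involved, so the check is a comparison of texts.

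1. **Scope in 2.3.1.** The class is significant neurologic disorders. *Progressive* stands inside the list of examples and attaches to multiple sclerosis. The list is explicitly not exhaustive.

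2. **Scope in criterion 13.** The class is significant *progressive* neurologic disorders. The list is again not exhaustive, but any addition to it must be progressive. The four named diseases are the same in both places, so all four are excluded outright under either text. The texts differ only for significant disorders that are not progressive; a stable seizure disorder is an example of mine, not the protocol's.

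3. **Other specific criteria.** Section 5.2 lists criteria 1 to 32, and only criterion 13 names neurologic disorders. The nearest others are criterion 4 (suicidal ideation and behaviour) and criterion 29 (alcohol or drug abuse), and neither reaches a neurologic diagnosis.

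4. **Remaining routes.**
   - Criterion 14 can exclude such a person, but only if the Investigator judges that the condition confounds the data or poses unacceptable risk.
   - Criterion 17 with 6.4.1 can exclude a person because of treatment. Drugs must be stopped 7 days before dosing (14 days for a potential enzyme inducer), or 5 half-lives if longer, and not resumed until after follow-up. The exception is a drug that the Investigator and sponsor judge will not interfere. Table 2 also bars systemic immunomodulators and biologics. This route acts on the drug and not on the disorder. It does not reach an untreated person, and both criterion 17 and the end of 6.4.1 allow case-by-case permission.

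5. **How other risk rows are carried over.** Suicidality becomes criterion 4. Pgp inhibitors and narrow-therapeutic-index CYP3A4 substrates become criterion 17 with Table 2. Keloid scarring, anaesthetic allergy and platelet count become criteria 32, 30 and 24. The CNS row is also carried into a specific criterion, but with a narrower class and no reason given. That pattern suggests a drafting slip, though it does not prove one.

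**The case against.** The strongest reply is that criterion 14 already does the work. Eligibility requires that none of the 32 criteria apply, so passing criterion 13 does not admit anyone, and criterion 14 comes next. *Significant* is undefined in both texts, so 2.3.1 also calls for clinical judgement, and widening criterion 13 partly replaces one judgement with another. Most of this stands, and it is why the practical gap is small. It does not remove the mismatch. Under 2.3.1, finding a significant neurologic disorder is enough to exclude; under criterion 14 the Investigator must also find confounding or unacceptable risk. A criterion confined to progressive disease may also be read as a sign that stable disease is acceptable.

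A second reply is that the four shared examples suit a progressive class, so the risk table may simply be loosely worded. That is possible. The documents do not settle which text was intended, only that the two disagree.

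Three stronger readings are tempting but not supported:

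- **That criterion 14 is the only route to exclusion.** It is not: criterion 17 with 6.4.1 can also stop a medicated person, including one with a treated seizure disorder.
- **That Section 5 formally overrides 2.3.1.** Appendix 2 does say "Protocol-specific requirements for inclusion or exclusion of participants are detailed in Section 5 of the protocol", but that is a cross-reference in the laboratory-test appendix and does not rank the sections. Section 5.2 matters because it is the list that sites confirm at Screening.
- **That participants are left unprotected.** Screening includes medical history and a full physical examination that covers the neurological system (1.3 and 8.2.1), and CNS adverse events are monitored. The 13-week animal studies showed no neurological events, the 39-week monkey study showed no CNS findings, and the CNS row reports no drug-associated CNS adverse events in clinical studies.

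**Conclusion.** The point holds as a minor internal inconsistency, wrong as written, in a safety eligibility rule. It is a mismatch between two parts of the protocol and does not show that a design decision is unsound. A person with a significant non-progressive neurologic disorder is not excluded for that disorder by any specific criterion, although 2.3.1 says that person will be.

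Its size cannot be estimated. The documents give no prevalence of such disorders among people screened, and the number affected may be zero. Sample size, power and the primary analysis are unaffected.

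The conclusion rests on the ordinary grammatical reading of the two sentences and on all 32 criteria, which are visible. Confidence is high that the texts differ; it is not high that any participant would be harmed as a result.

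**What to change.** In criterion 13, delete the word *progressive* where it precedes *neurologic disorders*, and leave the four examples unchanged, including progressive MS. The class then matches 2.3.1. Make the same change in any site checklist built on the criterion. Optionally, add to criterion 13 or 14 a prompt for the Investigator to consider susceptibility to neurologic effects, which 2.3.1 also promises. If the sponsor meant progressive disorders only, narrow 2.3.1 instead and give the reason.

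The edit is one word, but it changes eligibility and so needs ethics approval like any amendment (10.1.1). It can go in with the next one. *Significant* remains a judgement, so sites may still differ on stable or long-resolved conditions.

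The other cost is possibly an occasional extra screen failure. Section 9.2 plans as follows: "Approximately 32 participants will be screened to achieve 21 randomly enrolled to either GSK2982772 or placebo in a 2:1 allocation ratio". That is a yield of 21/32 = 65.6%. As an illustration only, assume k further failures among those 32. The number to screen for 21 randomised is then 21 × 32/(21 − k):

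- k = 0: 672/21 = 32
- k = 1: 672/20 = 33.6, about 34
- k = 2: 672/19 = 35.4, about 36

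The values of k are assumptions, and nothing in the documents says which is likely.

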5.3. Lifestyle Considerations

Participants must adhere to the contraceptive requirements listed in Appendix 4.

CONFIDENTIAL

5.3.1. Meals and Dietary Restrictions

There are no meal or dietary restrictions except on the Day 1, 29 and 85 visits when participants should fast overnight prior to these visits.

5.3.2. Alcohol Consumption

Participants must abstain from alcohol for 24 hours before all study visits.

5.3.3. Sun Exposure and Activity

Participants must not sunbathe or use a tanning device (sun bed or solarium) for 28 days prior to Day 1 until the follow-up visit (Day 113). Participants will be advised that when they are outdoors they must wear protective clothing (e.g. sun hat, long sleeves) as well as use a broad spectrum UVA/UVB sunscreen and lip balm (sun protection factor [SPF] ≥30) on exposed areas.

Participants will abstain from strenuous exercise for 48 hours prior to each blood collection for clinical laboratory tests.

5.4. Screen Failures

Screen failures are defined as participants who consent to participate in the clinical study but are not subsequently randomized. A minimal set of screen failure information is required to ensure transparent reporting of screen failure participants to meet the Consolidated Standards of Reporting Trials (CONSORT) publishing requirements and to respond to queries from regulatory authorities. Minimal information includes demography, screen failure details, eligibility criteria, any protocol deviations and any SAEs.

Retesting in case of spurious results or sample handling error at Screening is allowed.

Individuals who do not meet the criteria for participation in this study (screen failure) may be rescreened once if there is reasonable possibility that the individual would be eligible, in the opinion of the Investigator. Participants should be assigned a new participant number.

6. STUDY INTERVENTION

Study intervention is defined as any investigational intervention(s) to be administered to a study participant according to the study protocol.

ARM Name	GSK2982772	Placebo
Туре	Drug	Drug
Dose Formulation	Tablet	Tablet
Unit Dose Strength(s)	480 mg	NA
Dosage Level(s)	960 mg QD	NA
Route of Administration	Oral	Oral
Use	Experimental	Placebo- comparator
IMP and NIMP	IMP	IMP
Sourcing	Provided centrally by the Sponsor	Provided centrally by the Sponsor
Packaging and Labeling	Study Intervention will be provided in bottles. Each bottle will be labeled as required per country requirement.	Study Intervention will be provided in bottles. Each bottle will be labeled as required per country requirement.

6.1. Preparation/Handling/Storage/Accountability

- 1. The Investigator or designee must confirm appropriate temperature conditions have been maintained during transit for all study intervention received and any discrepancies are reported and resolved before use of the study intervention.
- 2. Only participants enrolled in the study may receive study intervention and only authorized site staff may supply or administer study intervention. All study interventions must be stored in a secure, environmentally controlled, and monitored (manual or automated) area in accordance with the labeled storage conditions with access limited to the Investigator and authorized site staff.
- 3. The Investigator, institution, or the head of the medical institution (where applicable) is responsible for study intervention accountability, reconciliation, and record maintenance (i.e., receipt, reconciliation, and final disposition records).
- 4. Further guidance and information for the final disposition of unused study intervention are provided in the Study Reference Manual (SRM).
 - Under normal conditions of handling and administration, study intervention is not expected to pose significant safety risks to site staff.
 - A Material Safety Data Sheet (MSDS)/equivalent document describing occupational hazards and recommended handling precautions either will be

provided to the Investigator, where this is required by local laws, or is available upon request from GSK.

6.2. Measures to Minimize Bias: Randomisation and Blinding

Randomisation

At Screening, a unique Participant Number will be assigned to any participant who has at least one Screening procedure performed, other than informed consent. The unique Participant Number will be used to identify individual participants during the course of the study.

Participants who meet Screening eligibility criteria will be randomised to a treatment group through an Interactive Web Response System (IWRS). Before the study is initiated, the log in information & directions for the IWRS will be provided to each site. The IWRS will confirm the participant's case report form (CRF) number (Participant Number) and provide the randomisation number, where:

• A randomisation number will be assigned from a randomisation schedule generated by Clinical Statistics, prior to the start of the study, using validated internal software.

Once assigned, this number must not be reassigned to any other participant in the study. The randomisation is centrally controlled by the IWRS.

Participants will be randomised to receive either GSK2982772 or placebo in a 2:1 ratio. The randomisation will be stratified by prior biologic use. Participants will take study medication every day, once a day for 12 weeks, at approximately the same time each day.

Participants will be administered the first daily dose of study medication by site staff during the site visit for Day 1 (Week 0). At subsequent visits, the dose should be taken either on site (preferred) after the pre-dose assessments, or after the visit at home only if the participant dosing at site would result in a treatment overdose (refer to Section 8.4). Participants will self-administer all other doses of study medication and will record the date and time in the diary cards provided to them. Returned study intervention should not be re-dispensed to the participants.

See the SRM for further details.

Blinding

This will be a double-blind study.

Access to participant-level unblinded data will be restricted to the GSK Biostatistics and CPMS members of the study team for the purpose of conducting analyses for the planned interim analysis. Summary-level data will be shared with the internal DRC at the interim analysis, membership of which will be listed in a data review charter. Results of the interim will not be shared outside of this committee, only the decision and its

implications will be communicated to the study team to minimise bias to the remainder of the trial.

CONFIDENTIAL

All other members of the GSK study team will remain blinded throughout the study.

The IWRS will be programmed with blind-breaking instructions. In case of an emergency, the investigator has the sole responsibility for determining if unblinding of a participants' intervention assignment is warranted. Participant safety must always be the first consideration in making such a determination. If the Investigator decides that unblinding is warranted, the Investigator should make every effort to contact GSK prior to unblinding a participant's intervention assignment unless this could delay emergency intervention of the participant. If a participant's intervention assignment is unblinded, GSK must be notified within 24 hours after breaking the blind. The date and reason that the blind was broken must be recorded in the source documentation and case report form as appropriate.

GSK's Global Clinical Safety and Pharmacovigilance (GCSP) staff may unblind the intervention assignment for any participant with an SAE. If the SAE requires that an expedited regulatory report be sent to one or more regulatory agencies, a copy of the report, identifying the participant's intervention assignment, may be sent to Investigators in accordance with local regulations and/or GSK policy.

